#### 12.8 CONFIDENTIALITY

All data and information collected during this study will be considered confidential. All data used in the analysis and summary of this study will be anonymous, and without reference to specific study subject names. Access to study subject files will be limited to authorized personnel or designees of Investigator, and research staff. Authorized regulatory personnel have the right to inspect and copy all records pertinent to this study. National regulations regarding confidentiality will be followed as appropriate.

### 13. INVESTIGATOR RESPONSIBILITIES, RECORDS, AND REPORTS

#### 13.1 GENERAL RESPONSIBILITIES

Principal Investigator at the site must:

- Assure compliance of all staff to the protocol
- Ensure all staff are trained to the protocol, TENS system and electronic diary
- Obtain and maintain a copy of the Institutional Review Board (IRB) approved Informed Consent form;
- Documentation of IRB approval of the final protocol (and amendments if applicable) providing evidence of the following:
  - o A statement of IRB approval for the proposed study at the institution
  - Clear identification of the reviewed documents (may be done by attaching review packet to approval letter)
  - The date the study was approved
  - A statement that the Informed Consent document (revision date referenced) has been approved (may be a separate documented letter)
  - A listing of any conditions attached to the approval
  - o Identification of the approved Principal Investigator at the site
  - o The signature of the IRB chairperson

Until the study is completed, the Investigator will advise the IRB of the study progress at least annually. Written approval from the IRB must be obtained yearly to continue the study. Any amendments to the protocol, as well as associated consent form changes, will be submitted to the IRB and written approval obtained prior to implementation. Serious adverse event reports will be submitted as requested by the IRB.

#### 13.2 INFORMED CONSENT

A copy of the Informed Consent must be forwarded to the IRB. All study subjects must provide written informed consent using an IRB-approved Informed Consent. The study must be explained to the study subjects in English. The Principal Investigator at the site, or designated representative, must be available to answer all of the study subject's study-related questions. Study subjects will be assured that they may withdraw from the study at any time for any reason and receive alternative conventional therapy as indicated.

#### 13.3 PROTOCOL DEVIATIONS

A Protocol Deviation is defined as an event where the Investigator or site personnel did not conduct the study according to the Protocol.

Investigators must approve any major deviations from the Protocol, except where necessary to protect the life or physical well-being of a subject in an emergency. Such approval shall be documented in writing and maintained in clinical study management files. Prior approval is generally not expected in situations where unforeseen circumstances are beyond the Investigator's control; however, the event is still considered a deviation and must be reported on the appropriate Case Report Form (CRF).

Deviations must be reported to the PI regardless of whether medically justifiable, pre-approved or performed to protect the subject in an emergency. Subject-specific deviations will be reported on a Protocol Deviation CRF.

Regulations require that the PI and site maintain accurate, complete and current records, including documents showing the dates of and reasons for each Protocol Deviation. For reporting purposes, Protocol Deviations are defined as major and minor as follows:

Major Deviation: Any deviation from subject Inclusion and Exclusion

criteria, subject Informed Consent procedures or

authorized device use.

Minor Deviation: Deviation from a protocol requirement such as

incomplete/inadequate subject testing procedures, follow-ups performed outside specified time windows,

etc.

Minor Deviations that continue to occur may be classified as Major Deviations if corrective action is not taken to secure future compliance to the Protocol.

#### 13.4 REPORTING REQUIREMENTS

As required by the IRB, the Investigator is responsible for reporting study progress to the IRB at least annually. The Investigator/Sponsor, as required by the local regulations, should notify the IRB in writing after completion, termination, or discontinuation of the study at the site. If the study is discontinued due to safety concerns, the Investigator will notify the IRB immediately. Timelines for notification are dependent on IRB requirements.

#### 13.5 SOURCE DOCUMENTS

Source documents are defined as original documents, data and records. These may include hospital records, clinic and office charts, laboratory data/information, and recorded data from automated instruments, subject-reported data collected from the diary and transmitted to the secure database, microfiches, photographic negatives, microfilm or magnetic media, and/or x-rays.

The Investigator shall maintain all source documents as required by the Protocol, including laboratory results (e.g., pregnancy tests), subject report forms, supporting medical records, and Informed Consent forms for at least seven (7) years after the study is terminated or according to site and country specific requirements.

#### 13.6 Access to Source Data/Documents

The Investigator/institution will permit direct access to source data/documents in order for IRB review and regulatory inspections to be performed. These data may be shared with regulatory agencies.

#### 13.7 DATA COLLECTION

Required data for this study will be captured on standardized CRFs. CRFs will be completed and stored for data analysis. Any deficiencies identified on the CRF will be communicated to the PI by the Clinical data Monitor as appropriate.

#### 13.8 ON-SITE AUDITS

The Investigator and/or designee must be available to respond to reasonable requests and audit queries made by authorized regulatory representatives during the audit process.

#### 14. SITE MONITORING PROCEDURES

A Clinical Data Monitor will be responsible for the monitoring of this study. Responsibilities may be shared with Investigator or designee and include:

- 1. Conducting site initiation visits (training to product and protocol) after Institutional Review Board (IRB) approval and before first subject enrollment.
- 2. Maintaining regular contact with the site through telephone contact, email and on-site visits.
- 3. Assuring that the Protocol is followed; verifying that complete, timely and accurate data are submitted.
- 4. Monitoring subject data, including: reviewing Case Report Forms (CRFs) for completeness, verifying data to source documentation including operator worksheets retained with CRF documentation and hospital charts, and addressing problems with inconsistent, illegible and/or incomplete data.
  - 5. Assuring that the Investigator's study file is maintained and that the site facilities continue to be adequate.
  - 6. Conducting a close-out visit after completion of all CRFs.

During the study, the study site will be visited periodically by the Clinical Data Monitor. The Clinical Data Monitor will ensure Protocol compliance, accurate recording of results, reporting of adverse events, and record keeping. The Clinical Data Monitor will evaluate and summarize the results of each site visit in written reports, identifying any repeated data problems with any Investigator and specifying recommendations for resolution of noted deficiencies.

#### 15. DATA QUALITY ASSURANCE

Standard Case Report Forms (CRFs) will be provided for use at all investigational sites. The Investigator is responsible for completion and timely submission of the forms for monitoring data processing. For subject reported outcome information recorded by the subject using the diary, an audit trail will ensure any changes made to the data are properly attributed and have been reviewed and approved by the Investigator.

A Database containing data obtained from the CRFs and diary data from the handheld diary will be maintained by the PI, The management of these data will be compliant with the relevant parts of United States (US) CRF data regulations, including CFR Part 11.

Data processing will be performed by the Clinical Data Monitor.

Quality assurance procedures are designed to ensure that complete, accurate and timely data are submitted, that Protocol requirements are followed, and that complications, Adverse Events (AEs) and adverse device effects (ADE) are correctly reported.

Incoming data are reviewed to identify inconsistent or missing data and AEs/ADEs. Any data issues will be addressed with the Principal Investigator at the site. All hard copy forms and data files will be secured to ensure confidentiality.

#### 16. ETHICAL REQUIREMENTS

#### 16.1 DECLARATION OF HELSINKI

The study will be performed in accordance with ISO/EN 14155, parts 1 and 2, recommendations guiding physicians in biomedical research involving humans adopted by the 18th World Medical Assembly, Helsinki, Finland (1964 and later revisions), United States Food and Drug Administration (FDA) regulations, and International Congress on Harmonization (ICH) and Good Clinical Practice (GCP) guidelines.

It is the responsibility of the Principal Investigator at the site to obtain approval of the study protocol from the competent Institutional Review Board (IRB) and to keep them informed of any Serious Adverse Events (SAEs), serious adverse device effects, and Protocol amendments. All correspondence with the IRB should be filed by the Investigator

#### 16.2 SUBJECT INFORMATION AND CONSENT

It is the responsibility of the Investigator to give each subject full and adequate verbal and written information regarding the objectives and procedures of the study and the possible risks involved, and to obtain signed Informed Consent from all subjects prior to inclusion in the study unless the subject's health condition does not allow Informed Consent, in which case the national procedures will be applied.

The original, signed Informed Consent is filed with the subject study records, and a copy is provided to the subject.

#### 16.3 SUBJECT DATA PROTECTION

The subjects will be identified in the Case Report Forms (CRFs) with a unique subject number and initials.

Per applicable regulations, the subject must be informed that the data will be stored and analyzed by computer, that national regulations for handling of computerized data will be followed, and that only the Investigator and designated research staff will have access to individual subject data. Furthermore, the subjects should be informed about the possibility of inspection of relevant parts of the hospital records by Health Authorities.

#### 16.4 REPORTING AND COMMUNICATION OF RESULTS

All information and data generated in association with this study will be held in strict confidence and remains the sole property of PI.

#### 16.5 CLINICAL TRIAL TERMINATION

A subject's participation in the clinical trial will be terminated if the Investigator believes it is in the subject's best medical interest or if the subject no longer complies with the clinical trial requirements. The subject may also decide to withdraw from the clinical trial at any time and terminate participation. The IRB and/or other Regulatory Authorities may decide to interrupt this clinical trial if either believes that this is necessary.

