#### 5. STUDY DESIGN

Randomized, adaptive parallel arm study. Subjects will be initially screened during a screening period (1 week, ±7 days; Figure 2). During this screening period, prior to study procedures being performed, subjects will sign an informed consent form. Then they will have their

[figure not shown]

Figure 2: Study Outline

weight and blood pressure measured, FOCBP will have a pregnancy test, get blood drawn for analysis (blood lipids, CMP, hemoglobin A1c), and complete patient preference questionnaires. At the end of the screening/baseline period, eligible subjects will be offered the chance to enroll in the study. After enrolling, subjects will be randomized to treatment or control groups.

The Treatment group will be instructed to follow a healthy 1200 calorie diet that they will follow for the duration of the study and will receive training on the use of the weekly paper diary, electronic scale, smartphone app and the Elira wearable patch system. All treatment subjects will be required to stimulate in the office for a period of time to confirm sufficient system training and tolerability of the stimulation. Following this, subjects will enter the Therapy Period, for a 12-week duration.

The Control group will be instructed to follow a healthy 1200 calorie diet that they will follow for the duration of the study and will receive training on the use of the weekly paper diary and electronic scale. The Control group will not receive the electronic smartphone app or the Elira wearable patch system.

At the end of the Therapy Period, subjects will be assessed for weight loss, blood pressure, CMP, blood lipids, HbA1c, and will be terminated from the study.

The study utilizes an adaptive approach where cohorts of enrolled subjects (in groups of 25 per arm) are assessed for dose response and progression to achievement of primary and secondary endpoints. Frequent interim endpoint assessment utilizing Markov-chain Monte Carlo (MCMC) methods coupled with longitudinal analyses will be utilized to determine sample sizes for future cohorts (assessed primarily via Normal dynamic linear modeling [NDLM]).

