#### 5.1 Dosing Schedule

All Treatment Subjects will be trained in rotation of the patch electrodes every 24h such that it is applied to varying locations on the T6/T7 dermatome. Each active therapy subject will receive up to 30 mA sustained current of stimulation (up to 40mA peak) for 30 minutes after each of three meals per day (delivered within 1-hour post prandially). Based on tolerance of the therapy, a subject may decrease his or her dose by dropping one of the 3 post prandial sessions after receiving approval from a clinical coordinator and/or PI. Subjects who do not experience sufficient appetite suppression may add up to three 15-minute pre-prandial rescue sessions delivered within 2 hours before each meal after receiving approval from a clinical coordinator and/or PI. The nominal stimulation dose per day for any subject will thus be 2400 mA (60 minutes at 40 mA) while the maximum dose for any given subject will be 5400 mA (135 minutes at 40 mA).

During the therapy period, Treatment Subjects will undergo initial assessments to ensure they are familiar with the device, the daily electronic diary, weekly paper diary, and the 1200 calorie diet. All subjects (Treatment and Control) will be required to undergo follow-up assessments at least once per every 4 weeks during the study. Up to two additional unscheduled visits per subject will be permitted during the study. PI will oversee any adjustments to treatment dosing or stimulation parameters.

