#### 7.3 SELECTION AND ENROLLMENT OF SUBJECTS

Prospective study subjects will be screened for study eligibility. A subject is considered enrolled after:

- 1. Written Informed Consent is obtained.
- 2. Meeting all inclusion and exclusion criteria and randomized into the study.
- 3. This study will utilize unique subject numbers for the purpose of trial data collection. Subjects signing an Informed Consent but not meeting all criteria will not be considered enrolled in the study but the signed Informed Consents will be maintained by the PI for seven (7) years.

Following enrollment, subjects should remain in the study until completion of the required Therapy Phase.

A subject's participation may be discontinued for the following reasons:

- Subject Withdrawal: As subject participation in a clinical trial is voluntary, the subject may choose to discontinue participation at any time without penalty or loss of benefits.
- Investigator Termination: The Investigator may terminate the subject's participation without regard to the subject's consent if the Investigator believes termination is medically necessary.
- Lost-to-Follow-up: A subject is lost-to-follow up if he/she does not complete required follow-up, but has not "officially" withdrawn consent. In order to consider a subject lost to follow-up, site personnel should make all reasonable efforts to locate and communicate with the subject. A minimum of three (3) attempts to contact the subject should be recorded in the source documentation including date, time and name of site personnel attempting to make contact.

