#### 9.11 ELECTRONIC DAILY DIARY DEVICE

For Treatment Group Subjects only, an Android Smart Phone running a semi-custom daily diary application to capture hunger, calories, and weight will be provided. Subjects will be instructed on use by PI or designee.

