### 18.6 APPENDIX 6: SCHEDULE OF EVENTS

[figure not shown]
STUDY PERIOD	SCREENING/ BASELINE	ENROLLMENT/ RANDOMIZATION		END OF STUDY 		
VISIT #	VISIT 0	Visit 1	VISIT 2	VISIT 3	VISIT 4	VISIT 5
WEEK#	-1 WEEK	WEEK 0	WEEK 1	WEEK 4	WEEK 8	WEEK 12
VISIT WINDOW 	±7 Days	±7 Days	±7 Days	±7 Days	±7 Days	±7 Days
Informed Consent	Х					
Inclusion/Exclusion Criteria	Х	х				
Medical History	Х					
Diet History	Х					
Physical Exam	Х					Х
T6/T7 dermatome assessment	X 	X 	X 	X 	X 	X 
Blood Pressure	Х	х	х	х	Х	Х
Concomitant Medication Review	Х	х	Х	х	Х	Х
Height	Х					
Weight	Х	х	х	х	Х	Х
Laboratory Requisition - Blood Tests 	Х					Х
Urine Pregnancy Test (WOCBP)	Х	X e				Х
Administration of Patient Preference Survey	Х					Х
Administration of PHQ-9	Х					Х
Administration of TFEQ-R18V2		х	х	х	Х	Х
Provide/Train on Paper Diaries 	Х	х	х	х	Х	
Collect and Review Paper Diaries 		х	х	х	Х	Х
Randomization 		х				
Encourage 1200 calorie diet		х	х	х	Х	
Provide Electronic Scale		х				
Provide and Train on Electronic Diary 		х	х	х	Х	
Collect and Review Electronic Diary 			х	х	Х	Х
Provide and Train on TENS Unit and Patches 		x	x	х	х	
Collect and Examine TENS Unit and Patches 			х	х	х	Х
Provide/Instruct on TENS Clean-Cote Skin Wipes and/or Alcohol Prep Pads 		х	х	х	х	
Provide/Instruct on Cetaphil Lotion 		х	Х	х	Х	
Assessment of Adverse Events	Х	х	Х	х	Х	Х
Assessment of Adverse Device Effects 		х	Х	х	Х	Х
Schedule next visit	Х	х	Х	х	Х	
Study Exit						Х

All visits are ± 7 days
 Blood tests include HbA1c, lipid panel, CMP
 To be completed for control and treatment group

 To be completed for treatment group only 5 – Randomization into control or treatment group

 Complete UPT only if not completed at screening
7 – Complete all procedures at End of Study or Early Termination Visit

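### Section 16.5 ends participation for non-compliance, which Section 7.3 does not list; a non-compliant subject then has an exit weight in place of the Week 12 weight

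*Combined protocol and SAP*

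**What the plan says.** Section 16.5 (Clinical Trial Termination) makes ending participation mandatory in two cases: when the investigator judges it to be in the subject's best medical interest, or "if the subject no longer complies with the clinical trial requirements". It does not say which requirements count or how much non-compliance is enough.

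Section 7.3 gives three reasons for discontinuation: subject withdrawal, investigator termination and loss to follow-up. Its investigator clause is confined to medical need: "The Investigator may terminate the subject's participation without regard to the subject's consent if the Investigator believes termination is medically necessary". It also sets an expectation of retention: "Following enrollment, subjects should remain in the study until completion of the required Therapy Phase".

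For a subject who leaves early, footnote 7 of the Schedule of Events (Appendix 6) says: "Complete all procedures at End of Study or Early Termination Visit". Weight is one of those procedures. No section schedules a Week 12 weight after participation has ended.

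Section 8.3 keeps the partial data of dropouts and imputes by last value carried forward. Section 8.4 bases the effectiveness analyses on a modified intent-to-treat (MITT) population, meaning those who began their first Treatment Period visit, and adds a completer analysis restricted to subjects who completed every visit.

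The duties of the two arms differ. Treatment subjects stimulate "for 30 minutes after each of three meals per day (delivered within 1-hour post prandially" and are "trained in rotation of the patch electrodes every 24h" (Section 5.1). Section 9.11 adds: "For Treatment Group Subjects only, an Android Smart Phone running a semi-custom daily diary application to capture hunger, calories, and weight will be provided". Section 5 states: "The Control group will not receive the electronic smartphone app or the Elira wearable patch system". Section 5.3 makes the trial open label.

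**The concern.** The primary endpoint is percent change in body weight at the end of the 12-week Therapy Period, compared between arms. Whether people keep using the device and keep to the diet is part of what that comparison should reflect. A rule that ends participation for non-compliance replaces an obtainable Week 12 weight with an earlier one, for a reason that is itself likely to be related to weight loss.

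Two features add to the worry. First, only the treatment arm has sessions, patches and a phone diary, and the Section 9 table has staff review stimulation sessions and electronic diary use at each therapy visit in that arm alone. There is more to fail at, and failure is easier to see. Second, the staff who apply an undefined rule know the allocation.

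At stake are the meaning of the primary weight for terminated subjects and the comparability of the arms among completers. The primary safety endpoint is also affected: Section 8.1.1 defines it through the therapy phase, and scheduled adverse event visits stop when participation ends.

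**Working it through.** **1. The two rules side by side.**

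| | Section 7.3 | Section 16.5 |
|---|---|---|
| Investigator may or must end participation | If medically necessary | If in the best medical interest, or for non-compliance |
| Force | Permissive | Mandatory |
| Non-compliance listed | No | Yes, undefined |
| Retention | Subjects should stay to the end of the Therapy Phase | Not addressed |

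Two sites could treat the same non-adherent subject differently, and each could point to the protocol.

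**2. What happens to a terminated subject's weight.** The Early Termination visit records a weight. In the primary analysis that weight is the last value and is carried forward, provided the subject had reached the first Treatment Period visit. In the completer analysis the subject is excluded.

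**3. Primary MITT analysis: direction of the shift.** Assume that a fraction f of the treatment arm only is terminated at week w (4 or 8). The shift is the change in the treatment arm's mean loss compared with using the true Week 12 weight.

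- Loss continues linearly to a Week 12 value L, taken as 3.5% or 7.5% (the Section 8.2 means): shift = f × L × (w/12 − 1). Smallest: 0.10 × 3.5 × (8/12 − 1) = −0.12. Largest: 0.30 × 7.5 × (4/12 − 1) = −1.5. Both go against the device.
- Loss at a rate of 3.5% per 12 weeks up to exit, then full regain by Week 12: shift = f × 3.5 × w/12. Smallest: 0.10 × 3.5 × 4/12 = +0.12. Largest: 0.30 × 3.5 × 8/12 = +0.70. Both favour the device.

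The sign depends on what happens after exit, which is what the plan does not observe. Both sensitivity analyses in Section 8.3 impute the same outcome in the two arms, so neither tests missingness that differs by arm.

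**4. Completer analysis: illustration.** The plan gives no figure to reproduce here. Section 8.2 supplies an SD of 5 points, 75 per arm and 30% dropout, hence 75 × 0.70 = 52.5 completers per arm. The following are assumptions without a basis in the documents: no true device effect; a share p of the treatment arm only terminated, 10 to 20%; correlation r of 0.3 to 0.5 between non-compliance and poorer weight loss.

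Shift in the completer mean = r × SD × φ(z_p)/(1 − p), where φ is the standard normal density and z_p the point that cuts off p.

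- p = 0.10, r = 0.3: 0.3 × 5 × 0.1755/0.90 = 0.29
- p = 0.20, r = 0.5: 0.5 × 5 × 0.2800/0.80 = 0.87

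Standard error = 5 × √(2/52.5) = 0.98.

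Chance of a false positive favouring the device = P(Z > 1.96 − shift/SE):

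- 1.96 − 0.30 = 1.66, giving 4.8%
- 1.96 − 0.90 = 1.06, giving 14.4%

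The nominal one-sided rate is 2.5%. If the terminations come on top of the 30% dropout, the treatment arm has 52.5 × 0.90 = 47.25 or 52.5 × 0.80 = 42 completers. The standard errors become 1.00 and 1.04, and the rates 4.8% and 13.2%, so the range hardly moves.

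A second parameterisation agrees. If terminated subjects lose 4 points less than those kept, the bias is 0.10 × 4 = 0.4 or 0.20 × 4 = 0.8 points.

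**The case against.** The strongest reply is that the plan already handles these subjects. They are weighed at the Early Termination visit, their partial data are kept, and the primary analysis is MITT, with completers only an additional analysis. This stands. A reader might infer that terminated subjects vanish from the primary analysis, or that the primary result is biased towards the device. The documents support neither: the subjects stay in through the carried-forward weight, and step 3 shows shifts in both directions.

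A reader might also infer that poor adherers are in fact removed unequally. The documents do not show this. The requirements are undefined and there are no rates by arm. Several duties bind controls as well: the diet, the paper diary, the visits, stable medication (Section 9.7) and contraception (Section 7.1.9). Not every lapse need be a breach either. Section 2.1 lets subjects reduce or stop stimulation for intolerable side effects, Section 5.1 permits an approved session drop, and Section 9.10 words the diet as encouragement. Unequal removal remains a plausible inference from the extra duties and closer checking in one arm, no more.

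Nor does Section 7.3 say that its list is exhaustive, so it does not forbid what Section 16.5 requires. That softens the conflict without removing it: one section mandates an exit that the other neither lists nor fits with its retention aim.

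Finally, weights from Weeks 1, 4 and 8 and the exit visit could support model-based imputation, and Section 8 allows multiple imputation. That is fair, but such a model would rest on untestable assumptions about what happens after exit, whereas the Week 12 weight could often simply be measured.

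**Conclusion.** The point holds in a limited form. Sections 16.5 and 7.3 disagree and must be reconciled. Followed as written, Section 16.5 puts an exit weight in place of the primary-endpoint weight for non-compliant subjects. In the primary MITT analysis the effect has no fixed direction: −0.12 to −1.5 points or +0.12 to +0.70 points under the two sets of assumptions tried. In the completer analysis only, with terminations confined to the treatment arm and the assumed inputs above, the bias is 0.3 to 0.9 points in the device's favour and the one-sided false-positive rate about 5 to 14%. These sizes illustrate the problem; they are not estimates, because the plan gives no termination rate or threshold. Terminations in the control arm, set to zero here, would offset some of the completer bias. This is a should-fix point: the primary analysis retains these subjects, but the missing weights are avoidable and cannot be collected afterwards.

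**What to change.** 1. Reconcile Section 16.5 with Section 7.3 so that one set of reasons for ending participation applies. Which reasons those are is for the sponsor and the investigators to decide.
2. State that stopping or reducing study therapy, or not keeping to the diet, is separate from leaving the study. Every randomised subject who has not withdrawn consent is asked to attend the scheduled weight and adverse event visits through Week 12, subject to the investigator's medical judgement. Decisions on stimulation stay with the investigator.
3. Use the Week 12 weight so obtained in the effectiveness analysis, in place of a carried-forward exit weight.
4. Report terminations by arm and reason. Section 13.3 is not the place to log subject non-adherence as it stands, because it defines deviations as acts of the investigator or site staff.

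The cost is a few sentences of protocol text, some extra follow-up effort for non-adherent subjects at visits already in the schedule, and a possibly less favourable estimate of the device's effect.
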